## **8.      CHANGES FROM METHODS PLANNED IN THE PROTOCOL**

The following exploratory analyses have been added:

- Change and percent change from Baseline in facial papule lesion counts at each visit
- Change and percent change from Baseline in facial pustule lesion counts at each visit
- Change and percent change from Baseline in facial nodule lesion counts at each visit
- Change from Baseline in overall Truncal PGA at each visit
- Proportion of subjects with at least 1-point decrease from Baseline in facial IGA at each visit

- Proportion of subjects with at least 1-point decrease from Baseline in overall Truncal PGA at each visit for subjects with Baseline overall Truncal PGA score of at least 1
- Proportion of subjects with at least 2-point decrease from Baseline in overall Truncal PGA at each visit for subjects with Baseline overall Truncal PGA score of at least 2
- Proportion of subjects achieving an overall Truncal PGA of clear (0) or almost clear (1) with at least a 2-grade decrease from Baseline at each visit for subjects with Baseline overall Truncal PGA score of at least 2
- Proportion of subjects achieving improvement (“Much better” or “Very much better”) according to the PGI-C at each visit
- Proportion of subjects achieving improvement (“A little better”, “Much better” or “Very much better”) according to the PGI-C at each visit
- Proportion of subjects achieving “Mild” or “Clear skin” according to the PGI-S at each visit
- Change from Baseline in PGI-S at each visit
- Proportion of subjects achieving “slightly satisfied”, “somewhat satisfied”, or “extremely satisfied” according to the SSQ at each visit
- Proportion of subjects achieving “slightly satisfied”, “somewhat satisfied”, or “extremely satisfied” according to the SSRS at Week 12 and Week 20
- Proportion of subjects achieving a DLQI of 0 or 1 at each visit for subjects with Baseline DLQI of at least 2
- Change from Baseline in PAS score based on blinded photographic assessment at each visit
- Change from Baseline in erythema score based on blinded photographic assessment at each visit

## 9. STATISTICAL SOFTWARE

The statistical software to be used for generation of the tables, listings, and figures is Statistical Analysis System® (SAS) version 9.4 or higher.

## 11. APPENDIX 1 DATA HANDLING RULES

The following table presents the algorithms to be used in SAS to calculate the derived variables, including rules for handling other missing data or partial dates, or irregular/unexpected data issues.

Category	Description	Data Handling Rules
1. Medical and Surgical History	Medical and Surgical History Beginning Date of Condition	
 
Missing day of begin date of condition will be imputed as the 1st of the month for the purpose of computing the onset day.
 
Missing month of begin date of condition will be imputed as June for the purpose of computing the onset day
 

	Medical and Surgical History End Date of Condition	
 
Missing day of end date of condition will be imputed as the 30th of the month for the purpose of computing the onset day.
 
Missing month of end date of condition will be imputed as June for the purpose of computing the onset day
 

2. First and Last Treatment Dates	Date/time of first and last dose of a study treatment	
 
The date and time (24 hr. clock) of the first dose of study treatment will be taken from the Dosing eCRF. The date of the last dose of study treatment will be the last date of dosing from the Dosing eCRF for the treatment.
 

3. Last Visit Date	Date of Last Visit	Date of last visit according to the Visit eCRF.
4. Last Study Participation Date (SDTM variable, typically named RFPENDTC)	Last Study Participation Date (SDTM variable, RFPENDTC), where SDTM denotes Study Data Tabulation Model	Last study participation date is defined as last known date of contact which is the later of the following dates: last visit date, date of the last dose, date of study completion or discontinuation, or death date.
5. Study Day Definitions	Study Day for assessment/event which occurs on or after the start of study treatment	Study Day = Date of assessment/event – date of the first dose of study treatment + 1.
	Study Day for assessments/events on days prior to the first dose of study treatment in the study	Study Day = Date of assessment/event – first dose date of treatment in the study.
	Study Day of Randomization	Study Day of Randomization = Date of randomization – date of the first dose of study treatment in the study + 1. Study Day is 1 if baseline day is on the day of randomization.
	First Dose Day	First Dose Day in the study is defined as the study day of the first dose of study treatment in the study (Study Day 1).
	Last Dose Day	Last Dose Day in the study is defined as the study day of the last dose of study treatment in the study (defined as the last date of dosing from the Dosing CRF pages).
	Last Study Day	For subjects who did not receive study treatment in the study (e.g., Non-Randomized subjects) , Last Study Day is defined as

Category	Description	Data Handling Rules
		(the later of the last visit date and the date of study completion or discontinuation from the End of Study CRF) – Date of Screening Visit + 1.  For subjects who received study treatment in the study , Last Study Day is defined as (the later of the last visit date and the date of study completion or discontinuation from the End of Study CRF) – first dose date in the study + 1.
	Days Since Last Dose for event (e.g., Death)	Days Since Last Dose is defined as date of event – date of last dose of study treatment.
6. Duration of event	The duration of any event	The duration of any event is defined as (stop date – start date + 1).
7. Prior and concomitant medication/treatment	Prior and concomitant medication/treatment	
 
1. Prior medication/treatment is any medication/treatment stopped prior to the first dose of study treatment (or the date of the randomization visit, Day 1, if the date of the start of study medication is missing). Medication/treatment continued into the treatment period will not be considered prior.
 
2. A medication/treatment will be identified as a concomitant medication/treatment if any of the following are true: 
 
• The start date or the end date is on or after the date of the start of study treatment (or the date of randomization, Day 1, if missing).
 
• The medication/treatment is checked as ‘Ongoing’, and the start date of the medication/treatment is prior to the first dose of study treatment (or the date of the randomization visit, Day 1, if the date of the start of study medication is missing).
 
• The start date and the end date are both missing
 
 
 

8. Adverse event	Treatment-emergent adverse event	If the AE start date is partial/missing, then 
 
• If AE start date is completely missing, then the AE is considered as treatment-emergent.
 
• If both AE start month and day are missing and AE start year is the same or after the first dose year, then the AE is considered as treatment-emergent.
 
• If AE start day is missing and AE start year and month are the same or after the first dose year and month, then the AE is considered as treatment-emergent.
 
 Missing/incomplete (partial) AE start and end dates will not be imputed for data listings.
	Missing relationship to study drug	For TEAE summary by relationship, a TEAE with a missing relationship to study drug will be considered as related.
9. Vital Signs	Multiple assessments for the same visit	If there are multiple vital sign values for the same parameter at a given visit, the last value will be chosen for analysis.

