8.2.1.4 TIME PERIOD AND FREQUENCY FOR EVENT ASSESSMENT AND FOLLOW-UP

The occurrence of an AE or SAE may come to the attention of study personnel during study visits and interviews of a study subject presenting for medical care, or upon review by a study monitor.

All AEs including local and systemic reactions will be captured on the appropriate eCRF. Information to be collected includes event description, date of onset, clinician's assessment of severity, seriousness, relationship to study treatment (assessed only by those with the training and authority to make a diagnosis), action taken, and outcome of the event. All AEs occurring while on study must be documented appropriately regardless of relationship (see [Section 8.2.1.3.2](#)). All AEs will be followed to adequate resolution.

Study site personnel will note the occurrence and nature of each subject's medical condition(s) present prior to the informed consent signature in the appropriate section of the source document and eCRF. During the study, site personnel will note any change in the condition(s) and the occurrence and nature of any AE. Care will be taken not to introduce bias when detecting AEs and/or SAEs. Open-ended and nonleading verbal questioning of the subject is the preferred method to inquire about AE occurrences.

Should a subject experience an AE at any time after the screening visit informed consent signature until the end of participation in the study, the event will be recorded as an AE in the source document and eCRF. Any SAE related to the study participation (eg, screening procedure) will be recorded in the source document and eCRF from the time consent is given to participate in the study until the end of participation in the study (EOS/ET visit).

Efficacy and Safety of Imsidolimab in Subjects with Acne Vulgaris
Protocol ANB019-209

Version 1.0
11 February 2021

Investigators are not obligated to actively seek AEs or SAEs after conclusion of the study participation. However, if the Investigator learns of any SAE, including a death, at any time after a subject has been discharged from the study, and he or she considers the event to be reasonably related to the study treatment or study participation, the Investigator must promptly notify the pharmacovigilance unit.

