9.4.8.1 ADVERSE EVENTS AND SERIOUS ADVERSE EVENTS

A TEAE is defined as:

- A new event that occurs during or after first dose of study treatment or,
- Any event present at Baseline that worsens in either intensity or frequency after first dose of study treatment.

Adverse events will be coded using the MedDRA and only TEAEs will be summarized. Number of events and percentage will be tabulated by preferred term (PT) and primary system organ class (SOC). Multiple occurrences of an AE for a subject will only be counted once per primary SOC and PT. Percentages will be determined relative to the subjects in the safety analysis set for the given treatment arm.

If the intensity or seriousness of the AE changes, the overall intensity or seriousness will be the maximum intensity or seriousness of the multiple occurrences. The TEAEs, SAEs, TEAEs leading to treatment discontinuation, and TEAEs leading to withdrawal of subject will be tabulated for each treatment arm.

All AE data will be listed for each subject.

Summaries over SOC and PT of TEAEs, TEAEs leading to death, SAEs, and TEAEs that led to discontinuation from the study or study treatment will be presented by treatment. Summaries will also be presented by relatedness to the study treatment and the severity of the TEAE.

9.4.8.2 12-LEAD ELECTROCARDIOGRAM, VITAL SIGNS, AND CLINICAL SAFETY LABORATORY TESTS

Summaries and listings of data for vital signs and safety laboratory tests result (hematology, biochemistry, and urinalysis) will be presented. Appropriate descriptive statistics will be summarized for the observed value at each scheduled assessment and for the corresponding change from Baseline.

For hematology and biochemistry tests, listings of subject data will also flag any abnormal or out-of-range values. Clinically significant changes in the laboratory test parameters will be summarized and listed. Hematology and biochemistry data will be reported in System International units.

Descriptive statistics will be used to present the safety outcomes including, weight, BMI, 12-Lead ECG, vital signs, and clinical laboratory test results.

Change from Baseline will also be summarized for vital signs, and clinical laboratory tests results.

All ECG data results (normal/abnormal) will be summarized using frequency and percentage, and parameter values will be summarized descriptively. Clinically significant abnormalities will be presented in by-subject listings.

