### **6.6.3 Adverse Events**

Adverse events experienced by the subjects will be collected throughout the entire study and will be coded using the version of the MedDRA specified in the approved Data Management Plan. Analysis of AEs will be carried out on the Safety Analysis Set.

An AE is considered treatment-emergent if the date of onset is during or after first dose of study treatment, or if the AE present at Baseline that worsens in either intensity or frequency after first dose of study treatment. An AE that begins on the same date as the first dose of study treatment is treatment-emergent if the AE begins on or after the time of first dose or if the time of AE onset is unknown.

The severity of AEs will be evaluated as “Mild”, “Moderate”, and “Severe” using the criteria specified in **Section 8.2.1.3.1** of the study protocol.

Adverse events will be classified as related, possibly related, unlikely to be related, or unrelated to study treatment using the criteria specified in **Section 8.2.1.3.2** of the study protocol. If the relationship to study treatment is missing, then the relationship will be set to “related” in the summaries of AEs.

Adverse events will be categorized as serious or non-serious using the definition specified in **Section 8.2.1** of the study protocol.

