#### **Events with Partial Onset Dates**

All treatment-emergent adverse events (TEAEs) will be included in the tabulations regardless of the completeness of the onset dates. Partial dates will be imputed in order to determine if an AE is treatment-emergent using the rules in **Appendix 1**; however, imputed dates will not be provided in the data listings.

**Uncoded Events:** Before the database lock, uncoded events will be assigned the string “UNCODED” as the body system, and the verbatim term will be used as the preferred term, so they can be included in the summary tables. In the final dataset, all the adverse events will have been coded.

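### For adverse events with a missing or partial start date, the SAP's treatment-emergent rule ignores the end date, so some events that ended before dosing are tabulated as TEAEs

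*SAP*

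**What the plan says.** SAP 6.6.3 defines the term by timing: "An AE is considered treatment-emergent if the date of onset is during or after first dose of study treatment", with a second limb for events present at baseline that get worse after it. Protocol 9.4.8.1 has the same two limbs, the first being "A new event that occurs during or after first dose of study treatment or".

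For incomplete onset dates, the SAP passes the decision to Appendix 1: "Partial dates will be imputed in order to determine if an AE is treatment-emergent using the rules in" that appendix. Item 8 then gives three rules, each ending in a treatment-emergent label:

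- Nothing known: "If AE start date is completely missing, then the AE is considered as treatment-emergent".
- Year only: "If both AE start month and day are missing and AE start year is the same or after the first dose year".
- Year and month only: "If AE start day is missing and AE start year and month are the same or after the first dose year and month".

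None of the three has a condition on the end date. Item 8 mentions end dates only to say that incomplete dates are left unimputed in the listings.

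Events before dosing are in the database. Protocol 8.2.1.4 starts recording at consent ("Should a subject experience an AE at any time after the screening visit informed consent signature until the end of participation"), and screening can last up to 30 days. Protocol 8.2.1.5 has the investigator record both start and stop dates.

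**The concern.** A missing-data convention is meant to settle cases that the record leaves open. Here the record may already settle the case, and the rule does not look.

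Take a made-up example: consent on 3 June, first dose on 25 June, start date known only as June, end date 10 June. Year and month match those of the first dose, so the third rule labels the event treatment-emergent. Yet it ended 15 days before dosing. It neither began nor worsened after the first dose, so it fails both limbs of the definition.

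At stake is the accuracy of the safety tables. SAP 7.9.2 restricts the summaries to TEAEs, so an event labelled this way is counted as if it followed treatment. If its causality field is also blank, SAP 6.6.3 and item 8 count it as related too.

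**Working it through.** The plan gives no figure on this point to reproduce. The check sets the rules against the definition and then asks how often the rules would mislabel a pre-dose event.

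**1. Rule against definition.** Consider an event that began after consent and ended before the first dose.

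| Start date recorded | Label under SAP as written | Label under SAP 6.6.3 definition |
|---|---|---|
| Complete | Not TEAE | Not TEAE |
| Month or year earlier than that of first dose | Not TEAE | Not TEAE |
| Day missing, same month and year as first dose | TEAE | Not TEAE |
| Only year known, same year as first dose | TEAE | Not TEAE |
| Completely missing | TEAE | Not TEAE |

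The last three rows conflict. Recurrence does not explain them, because Protocol 8.2.1.4 asks for onset and duration of each episode of an intermittent event.

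**2. Comparison within the same appendix.** Item 7 does use the stop date for medications: one stopped before the first dose is classed as prior. Item 8 has no counterpart for adverse events.

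**3. Share mislabelled, given an incomplete start date.** Assumptions: one-day events spread evenly over the 30 days before dosing, and first-dose dates spread evenly over a 365-day year. That gives 365 × 30 = 10,950 combinations of dose date and onset day.

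- *Start completely missing:* every event is labelled a TEAE, 10,950 / 10,950 = 100%.
- *Only year known:* the label is avoided only when onset falls in the previous calendar year. For a dose on January day d (1 to 30), 31 − d onset days do so, and these sum to 465. Share mislabelled = (10,950 − 465) / 10,950 = 95.8%.
- *Only day missing:* for a dose on day d of a month, d − 1 of the 30 preceding days lie in that month. Summed over a month this is 465 for 31 days, 435 for 30 days and 378 for 28 days. Over the year: 7 × 465 + 4 × 435 + 378 = 5,373. Share mislabelled = 5,373 / 10,950 = 49.1%. As a rough check, the mean of (d − 1)/30 over d = 1 to 30 is 14.5/30 = 48.3%.

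With the condition that a recorded end date before the first dose rules out the label, the share is 0% in all three cases.

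**4. Effect on a table.** About 120 subjects randomized 1:1:1 gives 120 / 3 = 40 per arm. One subject wrongly counted adds 1/40 = 2.5 percentage points to that arm's incidence, if the subject has no other event in that row. A preferred term at 2/40 = 5.0% would move to 3/40 = 7.5%. For a non-serious event, that crosses the threshold of more than 5% for the common-TEAE table in SAP 7.9.2.

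**The case against.** The strongest reply is that this is a deliberate, conservative default. Where timing or causality is unknown, the SAP counts towards treatment: an unknown onset time on the dosing day is treatment-emergent, and a missing relationship is taken as related. Over-reporting is the safer error. That stands wherever timing is truly unknown. It does not cover an event whose recorded end date already answers the question.

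The trigger is also narrow. The event must begin after consent, since conditions present at screening go to medical history (Protocol 8.2.1.4). It must also end before Day 1, have a known end but an incomplete start, and survive the query process in Protocol 10.1.8 and 10.1.9.1. This stands, and it keeps the point small.

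Three stronger readings are tempting, but the documents do not support them.

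- *That screening-period events in general become TEAEs.* Complete start dates are classified correctly under SAP 6.6.3, and partial starts in an earlier month or year are not labelled.
- *That the rule biases or materially dilutes the comparison of imsidolimab with placebo.* Events that ended before the first dose cannot be caused by treatment and should not favour an arm. Few of them would barely change a risk difference, and SAP 7.9.2 plans counts and incidences with no between-arm test.
- *That the error would be invisible.* SAP 7.9.2 lists all adverse events, and dates are not imputed there, so an incomplete start beside a pre-dose end would be seen by anyone who looked.

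Finally, the shares of 49%, 96% and 100% do not measure impact. They apply to a subset whose size the documents do not give and which may be empty.

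**Conclusion.** The point holds for adverse events with a missing or partial start date only. For those, item 8 can give a label that contradicts SAP 6.6.3 and Protocol 9.4.8.1 when the recorded end date precedes the first dose. This is a stated rule that misclassifies, not a missing detail.

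The likely consequence is a slight inflation of TEAE incidence and some noise in small arms, at 2.5 percentage points per wrongly counted subject. That figure assumes 40 subjects per arm; the conditional shares assume an even spread of onset and dosing dates. The number of affected records is unknown and probably small. Nothing here touches the efficacy analyses. The change is worth making because it is cheap, but no result has been shown to depend on it.

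**What to change.** Add one sentence to SAP Appendix 1, item 8: *An AE whose recorded end date (complete, or its known parts) shows that it ended before the date of first dose is not treatment-emergent, whatever is missing from its start date.*

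Keep the three existing rules for every other case, including an end date that is missing, ambiguous, or the same day as the first dose. The conservative default then still governs wherever timing is truly open.

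The cost is one sentence and one condition in the program. There is a small downside: a mis-entered end date on an event with an incomplete start could remove a real TEAE from the summaries. To guard against this, pre-dose end dates on such events should be checked in the routine data queries before lock.

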## 12. APPENDIX 2 SAS CODE FOR STATISTICAL ANALYSES

This section will be completed after examining the existing data and prior to the final signoff of this SAP.

Test	Template SAS Code for Modeling (SAS Version 9.4)
Linear Repeated Measures Analysis of Covariance for the primary endpoint	<pre> PROC MIXED METHOD=REML; CLASS SUBJECT TRT VISIT BASEFIGA; MODEL Y = BASE BASEFIGA TRT VISIT / DDFM=KR SOLUTION OUTP=OUT; REPEATED VISIT / TYPE = UN SUBJECT=SUBJECT; LSMEANS TRT VISIT / PDIFF CL ALPHA=0.1; ODS OUTPUT LSMEANS=MEANS; ODS OUTPUT DIFFS=DIFF; RUN; </pre> 
Where TRT is treatment, VISIT is the study visit number, BASEFIGA is the facial IGA score at baseline, and BASE is the baseline of outcome variable.

Negative Binomial with GEE using PROC GENMOD	<pre> PROC GENMOD; CLASS SUBJECT TRT VISIT BASEFIGA; MODEL Y= BASE BASEFIGA TRT VISIT / LINK=LOG DIST=NEGBIN; REPEATED SUBJECT=SUBJECT / TYPE=UN; LSMEANS TRT VISIT / DIFF CL ALPHA=0.1; ODS OUTPUT LSMEANDIFFS = LSDIFS ESTIMATES=EST LSMEANS=LSMEANS PARAMETERESTIMATES=PE; RUN; </pre> 
Where TRT is treatment, VISIT is the study visit number, BASEFIGA is the facial IGA score at baseline, and BASE is the baseline of outcome variable.

Impute Intermittent Missing using the Monte Carlo Markov Chain (MCMC) approach	<pre> PROC MI DATA=data_in SEED=20210710 NIMPUTE=100 OUT=LESION_MONO; BY BASEFIGA TRT; /*Assuming different treatment, baseline facial IGA has different distribution*/ MCMC CHAIN=MULTIPLE IMPUTE=MONOTONE; /*Only impute intermittent missing values*/ VAR AGE BASE LESION1 – LESION5; /*Impute lesion count from Week 2 to Week 20, with age and baseline as covariates*/ RUN; </pre>

Test	Template SAS Code for Modeling (SAS Version 9.4)
Multiple Imputation with FCS Method	<pre> PROC MI MIN=0 ROUND=1 SEED=20220118;   CLASS BASEFIGA TRT SEX;   FCS REGPMM(LESION2 = LESION1 AGE SEX TRT BASE BASEFIGA );   FCS REGPMM(LESION3 = LESION1 LESION2 AGE SEX TRT BASE BASEFIGA );   FCS REGPMM(LESION4 = LESION1-LESION3 AGE SEX TRT BASE BASEFIGA );   FCS REGPMM(LESION5 = LESION1 LESION4 AGE SEX TRT BASE BASEFIGA );   VAR LESION1 - LESION5 AGE SEX TRT BASE BASEFIGA; RUN; Add 'MAX=4' in the PROC MI statement if response variable is facial IGA score. </pre>
Combine Parameter Estimates for LSmeans	<pre> PROC MIANALYZE DATA=OUTREG;   BY VISIT;   MODELEFFECTS TRT; /* TRT IS THE VARIABLE FOR LS TREATMENT DIFFERENCES */   STDERR TRTERR; /* TRTERR IS THE STANDARD ERROR FOR TREATMENT DIFFERENCES */ RUN; </pre>
Logistic Regression with GEE using PROC GENMOD	<pre> PROC GENMOD DESCENDING;   CLASS SUBJECT TRT VISIT BASE;   MODEL Y= BASE TRT VISIT / LINK=LOGIT DIST=BIN;   REPEATED SUBJECT=SUBJECT / TYPE=UN;   LSMEANS TRT VISIT / DIFF CL ALPHA=0.1;   ODS OUTPUT LSMEANDIFFS = LSDIFS ESTIMATES=EST LSMEANS=LSMEANS PARAMETERESTIMATES=PE; RUN; Where TRT is treatment, VISIT is the study visit number, and BASE is the baseline of outcome variable. </pre>
Ordinal Logistic Regression using PROC LOGISTIC	<pre> PROC LOGISTIC;   CLASS TRT BASE BASEFIGA;   MODEL Y = TRT BASE BASEFIGA; RUN; Where Y is the ordinal outcome variable, TRT is treatment, BASEFIGA is the facial IGA score at baseline, BASE the baseline of outcome variable. Remove BASEFIGA from the model if outcome variable is facial IGA. </pre>

Test	Template SAS Code for Modeling (SAS Version 9.4)
Cochran-Mantel-Haenszel ANOVA statistics (row means score)	<pre>PROC FREQ;   TABLES BASEFIGA*TRT*X/CMH2 ALPHA=0.1; RUN; </pre> 
Where BASEFIGA is facial IGA at baseline, TRT is treatment, and X is the outcome variable.

Exact unconditional CI	<pre>PROC FREQ;   TABLES TRT*X/ RISKDIFF(CL=EXACT) ALPHA=0.1;   EXACT RISKDIFF; RUN; </pre> 
Where TRT is treatment, and X is the outcome variable.

Obtaining generalized risk difference	<pre>PROC FREQ;   TABLES TRT*X / ALL LIST MISSING ALPHA=0.1;   TEST SMDCR; RUN; </pre> 
Where TRT is treatment, and X is the outcome variable.

Weighted Kappa and confidence interval	<pre>PROC FREQ;   WEIGHT COUNT;   TABLES BASEFIGA*TRT*X/AGREE ALPHA=0.1; RUN; </pre> 
Where BASEFIGA is facial IGA at baseline, TRT is treatment, and X is the outcome variable.

Test of treatment difference for agreement	<pre>PROC FREQ;   TABLES BASEFIGA*TRT*X/CMH2; RUN; </pre> 
Where BASEFIGA is facial IGA at baseline, TRT is treatment, and X is the Cicchetti-Allison weight of outcome variable. Cicchetti-Allison weight = 1-abs(CHG)/(k-1), where k = number of categories of the outcome variable.

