APPENDIX 3: PATIENT GLOBAL IMPRESSION OF CHANGE

Overall, how would you rate the change in severity of your acne compared with how it was before you started taking the medication in this study?

1. Very much better
2. Much better
3. A little better
4. No change
5. A little worse
6. Much worse
7. Very much worse

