- Proportion of subjects in each response category for the PGI-S at each visit**

The PGI-S is a single-item question, which asks the subject to rate the current severity of AV (“Clear skin”, “Mild”, “Moderate”, and “Severe”).

For each treatment group, the number of subjects in each response category for the PGI-S will be calculated at each visit specified in the Schedule of Activities in **Table 2**. The proportion of such subjects will be calculated for each treatment group at each visit (Weeks 0, 2, 4, 8, 12, and 20) as:

$$\frac{\text{Number of subjects with PGI-S of "Clear skin" at Week } x}{\text{Number of subjects in treatment group with PGI-S at Week } x}$$

$$\frac{\text{Number of subjects with PGI-S of "Mild" at Week } x}{\text{Number of subjects in treatment group with PGI-S at Week } x}$$

$$\frac{\text{Number of subjects with PGI-S of "Moderate" at Week } x}{\text{Number of subjects in treatment group with PGI-S at Week } x}$$

$$\frac{\text{Number of subjects with PGI-S of "Severe" at Week } x}{\text{Number of subjects in treatment group with PGI-S at Week } x}$$

- **Proportion of subjects in each response category for the PGI-C at each post-Baseline visit**

The Patient Global Impression of change (PGI-C) is a single item, self-administered questionnaire, which asks the subject to rate the change in their symptom severity (“Very much better” to “Very much worse”).

For each treatment group, the number of subjects in each response category for the PGI-C will be calculated at each post-baseline visit specified in the Schedule of Activities in **Table 2**. The proportion of such subjects will be calculated for each treatment group at each post-baseline visit (Weeks 2, 4, 8, 12, and 20) as:

$$\frac{\text{Number of subjects with PGI-C of "Not at all bothered" at Week } x}{\text{Number of subjects in treatment group with PGI-C at Week } x}$$

$$\frac{\text{Number of subjects with PGI-C of "Very much better" at Week } x}{\text{Number of subjects in treatment group with PGI-C at Week } x}$$

$$\frac{\text{Number of subjects with PGI-C of "Much better" at Week } x}{\text{Number of subjects in treatment group with PGI-C at Week } x}$$

$$\frac{\text{Number of subjects with PGI-C of "A little better" at Week } x}{\text{Number of subjects in treatment group with PGI-C at Week } x}$$

$$\frac{\text{Number of subjects with PGI-C of "No change" at Week } x}{\text{Number of subjects in treatment group with PGI-C at Week } x}$$

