### **7.      STATISTICAL ANALYSIS**

#### **7.1      Data Handling Rules and Definitions, Including Handling of Missing Data**

Except where specified all continuous variables will be summarized with descriptive statistics (the number of non-missing values, mean, SD, median, first and third quartiles, minimum, and maximum). Where data have been logarithmically transformed for analysis, the summary statistics on the back-transformed data will include the geometric mean (calculated as  $\exp(m)$ , where  $m$  is the mean of the data on the log scale) and the coefficient of variation (CV; calculated as  $100\sqrt{\exp(s^2)-1}$ , where  $s$  is the SD of the data on the log scale). All categorical variables will be summarized with frequency counts and

percentages. Tabulations will be provided based on all subjects combined, as well as separately by treatment group.

Missing data will be maintained as missing in the analysis datasets, unless specified otherwise. For variables where missing data are imputed, the analysis dataset will contain a new variable with the imputed value and the original variable value will be maintained as missing.

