#### **7.5.2.9 Proportion of Subjects in Each Response Category for the PGI-S at Each Visit**

The frequency and percentage of subjects in each response category for the PGI-S will be summarized at each visit. The difference in distribution between each dose of imidolimab and placebo will be compared using a Wilcoxon rank-sum test and Somers' D statistic which may be interpreted as a generalized risk

difference. This will be performed over all subjects and within each stratum for facial IGA (Grade 3 or 4). The common risk difference will also be tested using a generalized CMH test (ANOVA for row means), adjusting for facial IGA at baseline (Grade 3 vs. 4).

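### The Somers' D template in SAP Appendix 2 includes the MISSING option, so any row with a blank rating would be ranked as a real outcome at the low end of the scale

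*SAP*

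**What the plan says.** SAP 7.5.2.9 states that, for PGI-S at each visit, the difference in distribution between each dose and placebo "will be compared using a Wilcoxon rank-sum test" and Somers' D, which is read as a generalized risk difference. This is done overall and within facial IGA strata, with a stratified CMH test alongside. SAP 7.5.2.10 applies the same approach to PGI-C, and SAP 7.5.3 applies it to SSQ and SSRS.

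The only Somers' D code is the Appendix 2 entry with "TABLES TRT*X / ALL LIST MISSING ALPHA=0.1", followed by a TEST SMDCR statement. The CMH entry for the same endpoints reads "TABLES BASEFIGA*TRT*X/CMH2 ALPHA=0.1", without MISSING. The other three PROC FREQ entries (exact unconditional CI, weighted kappa, test of agreement) also omit it.

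SAP 6.2.3 defines each PGI-S proportion over the "Number of subjects in treatment group with PGI-S at Week" in question, and each PGI-C proportion over the "Number of subjects in treatment group with PGI-C at Week" in question. SAP 6.2.4 does the same for SSQ and SSRS. SAP 7.1 says: "Missing data will be maintained as missing in the analysis datasets, unless specified otherwise". The FCS imputation in that section covers facial IGA and lesion counts only.

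The scales run in opposite directions. Protocol Appendix 2 codes PGI-S from 1 (Clear skin) to 4 (Severe), and SAP 6.1.1 treats these as Grades 1 to 4. Protocol Appendix 3 starts PGI-C at "1. Very much better" and ends at 7 for the worst change. Protocol Appendices 6 and 7 code SSQ and SSRS from 0 (extremely dissatisfied) to 6 (extremely satisfied).

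**The concern.** Somers' D compares ranks, so it matters where a blank value falls in the ordering. By standard PROC FREQ behaviour, which the documents do not state, MISSING makes a blank a valid table level that enters the statistics, and a numeric blank sorts below every code. A missed PGI-S or PGI-C rating would then count as the best possible result, and a missed SSQ or SSRS rating as the worst. No single deliberate rule for missing data would give both.

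Two things are at stake. The effect measure for four patient-reported endpoints could mix the drug effect with differences in missingness between arms. And for one endpoint at one visit, Somers' D and the CMH test could rest on different sets of subjects.

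**Working it through.** **Plan's own figure.** SAP 3.5 assumes 10% discontinuation before Week 12: 120 × (1 − 0.10) = 108 evaluable, 36 per arm. This reproduces. The documents give no figure for Somers' D and no split of missingness by arm.

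**Formula.** Let D = P(active better) − P(active worse) among rated subjects, so positive favours imsidolimab. Let m_a and m_p be the shares with a blank rating on active and placebo. With blanks ranked best (PGI-S, PGI-C), pairs of two rated subjects keep their order, pairs of two blanks tie, and mixed pairs go to the arm with the blank:

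D_MISSING = (1 − m_a)(1 − m_p) D + m_a(1 − m_p) − m_p(1 − m_a) = (1 − m_a)(1 − m_p) D + (m_a − m_p).

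For SSQ and SSRS, where blanks rank worst, the last term becomes (m_p − m_a).

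**Assumed PGI-S distributions** (Clear skin, Mild, Moderate, Severe; not in the documents): active 0.10, 0.35, 0.40, 0.15; placebo 0.05, 0.25, 0.45, 0.25.

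- P(active better) = 0.10 × 0.95 + 0.35 × 0.70 + 0.40 × 0.25 = 0.44
- P(active worse) = 0.05 × 0.90 + 0.25 × 0.55 + 0.45 × 0.15 = 0.25
- D = 0.44 − 0.25 = 0.19

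| Blank on active | Blank on placebo | Calculation | D with MISSING | Same, if true D = 0 |
|---|---|---|---|---|
| 0% | 0% | – | 0.190 | 0 |
| 10% | 10% | 0.81 × 0.19 | 0.154 | 0 |
| 5% | 15% | 0.8075 × 0.19 − 0.10 | 0.053 | −0.10 |
| 15% | 5% | 0.8075 × 0.19 + 0.10 | 0.253 | +0.10 |

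With an equal share m the factor is (1 − m)². At m = 0.10 it is 0.81, a 19% attenuation whatever the distributions. The unequal rows rest on an assumed split.

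**Check with counts.** Take 40 per arm with 4 blanks in each, and rated counts of 4, 16, 13, 3 on active and 1, 10, 18, 7 on placebo. Active is better in 631 pairs and worse in 246, a difference of 385. Rated only: 385/(36 × 36) = 0.297. With MISSING the mixed pairs cancel, giving 385/(40 × 40) = 0.241, which is 0.81 × 0.297.

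**Scale of the shift.** The tie-corrected null variance of D at 40 per arm, using the pooled assumed shares 0.075, 0.30, 0.425 and 0.20 (sum of cubes 0.112), is about (81/(3 × 40 × 40)) × (1 − 0.112) = 0.0150, so the standard error is about 0.12. A shift of 0.10 is about 0.8 of a standard error.

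**The case against.** The strongest reply is that nothing goes wrong unless PROC FREQ reads rows with blank ratings. No section says that a row is created for a missed visit. The SAP 7.1 rule is about not imputing; it makes such rows plausible but does not guarantee them. If missed visits have no record, or the input is already limited to rated subjects, MISSING has no effect. This stands, and the point must be stated conditionally.

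The code is also visibly a template. The opening of Appendix 2 says the section is still to be completed before signoff. The entry has no visit loop and no restriction to one dose versus placebo, both of which SAP 7.5.2.9 needs, so some subsetting has to be added anyway. That is fair, but nothing indicates that MISSING would be removed in the process.

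The rated-subject denominators are written for proportions, and no section defines one for Somers' D. Carrying them over is an inference. It is supported by the absence of MISSING from every other PROC FREQ template.

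The planned 10% is total discontinuation before Week 12. It is not the missing share at each visit, and the documents do not suggest that it differs by arm.

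A reader might infer that the SAP plans to rank dropouts as best responders, or that the PGI-S and PGI-C results will be biased in favour of the arm losing more subjects. The documents support neither. The body text points to rated subjects only, and a shift in D needs both blank rows and unequal missingness.

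**Conclusion.** The template as written conflicts with the SAP's body text and can give a wrong Somers' D. The condition is that rows with a blank rating reach the procedure.

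If they do and missingness is equal across arms, D is pulled toward zero by (1 − m)², or 19% at the planned 10%, with no spurious effect under the null. If missingness is unequal, D moves by the difference in shares: toward the arm with more blanks for PGI-S and PGI-C, and away from it for SSQ and SSRS. The 0.10 example depends on the assumed 5% versus 15% split, and the 0.19 starting value on assumed distributions.

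The reach is limited to Somers' D for two secondary endpoints (PGI-S, PGI-C) and two exploratory ones (SSQ, SSRS), whose testing SAP 3.3 already calls exploratory. The CMH template has no MISSING, and Appendix 2 has no Wilcoxon template, so neither test is shown to be affected. The primary MMRM does not use this code. The Somers' d applied to FCS-imputed data in SAP 7.1 has no blanks to act on. The correction is worth making because it is nearly free and the result should not depend on an unstated filter.

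**What to change.** In the Appendix 2 entry for the generalized risk difference, delete MISSING and restrict the input to subjects with a non-missing rating at that visit, for example with WHERE NOT MISSING(X), run for each dose versus placebo. Report the number with no rating, by arm and visit, as a separate row outside the statistics. LIST need not be removed for this correction.

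The cost is one option deleted and one restriction added in a section that is still to be completed, before the primary analysis snapshot. No endpoint, analysis set or sample size changes.
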